6.6 Participant Recruitment, Randomization and Blinding

- **Participant Recruitment**

- Participants will be recruited through a unified online advertisement campaign across platforms such as Facebook and Google. Interested individuals will click on the advertisement, which directs them to a screening form where they provide preliminary information relevant to the study eligibility criteria.

- **Randomization**

- Screening and Eligibility Confirmation: Upon submission of the screening form, potential participants will undergo an initial eligibility assessment based on predefined inclusion and exclusion criteria.
- Randomization Approach: Eligible participants will then be randomized into either the treatment or control group. This randomization is performed after the completion of the screening process and is based solely on the cancer type, ensuring an equal distribution of participants across different cancer categories within both groups.
- Implementation Details: The randomization process will be conducted using a computer-generated random allocation sequence to ensure impartiality and minimize selection bias.

- **Blinding and Unblinding**

- Efforts will be made to ensure that the trial intervention and control products are as indistinguishable as possible to maintain the integrity of blinding. This includes measures such as:
 - Standardization of software: Both the trial intervention and control software products will be delivered through the same app to minimize visual differences that could indicate the treatment assignment.

- Blinding of personnel: Personnel involved in the administration, assessment, and monitoring of participants will be blinded to the treatment assignment whenever possible. This includes investigators, outcome assessors, data analysts, and other relevant staff.

6.7 Trial Intervention Compliance

Measures will be employed to ensure and document trial intervention compliance.

- Participant Engagement Metrics: The software platform will be equipped with tracking features to monitor participant engagement. Key metrics may include:
 - Frequency of logins and sessions attended.
 - Duration of each coaching session.
 - Participation in interactive features such as progress tracking and sharing exercise exertion feedback.
- Participant Surveys or Feedback: Program feedback for the intervention will be collected after each session.
- Attendance Records: For live Coactive coaching sessions, attendance records will be maintained to track participant involvement and compliance with scheduled sessions.
- System Logs: The software will generate system logs capturing user activity, such as login times, session durations, and interactions within the software. These logs serve as objective documentation of participant engagement.

Mandatory documents to complete include:

- Patient Reported Outcomes: These outcomes include all primary, secondary and exploratory metrics as highlighted above.
- Participant Engagement Logs: These logs will capture key metrics related to participant engagement and compliance with the software and coaching.
- Attendance Records: Specifically for live coaching sessions, attendance records will document participant attendance and participation.

Source data and records used to document trial intervention compliance will include:

- Digital Platform Data: System logs and engagement metrics generated by the software.
- Participant Surveys/Feedback: Responses collected from participant surveys or feedback forms.
- Attendance Records: Records of participant attendance at live coaching sessions.

6.8 Concomitant Therapy

Complement Theory is an adjunct treatment along with undergoing cancer treatment.

Hence, the survivor continues the standard of care as is.

Section 7: DISCONTINUATION OF TRIAL INTERVENTION AND PARTICIPANT WITHDRAWAL FROM TRIAL

7.1 Discontinuation of Trial Intervention

Criteria for Permanent Discontinuation of Trial Intervention

- Participant Withdrawal: Participants may voluntarily withdraw from the trial intervention at any time for any reason. This may include personal preferences, intolerable side effects, or changes in health status that make continued participation undesirable.
- Adverse Events: Participants experiencing serious or intolerable adverse events related to the trial intervention may be discontinued from further participation in the intervention. Adverse events will be carefully monitored and managed.
- Disease Progression: If a participant experiences disease progression or other significant changes in health status that render the trial intervention ineffective or inappropriate, discontinuation from the intervention may be warranted. This may include worsening of cancer symptoms, disease recurrence, or development of new medical conditions impacting intervention efficacy.

- Non-Adherence: Participants who fail to adhere to the trial intervention protocol, including non-compliance with usage instructions for the Live coaching and software, will be discontinued from further participation in the intervention.
- Ineligibility: If a participant is found to be ineligible for continued participation in the trial intervention due to newly discovered medical conditions or other factors, discontinuation from the intervention may be necessary.

Participants who discontinue trial intervention may or may not be allowed to continue the trial, depending on the specific circumstances. In some cases, participants may continue to undergo follow-up assessments and data collection even if they discontinue the intervention. This allows for the evaluation of secondary outcomes, long-term effects, and safety monitoring following discontinuation of the intervention.

Temporary Discontinuation or Interruption of Trial Intervention

- Acute Medical Events: Temporary discontinuation may be warranted in the event of acute medical events such as hospitalization, surgery, or serious adverse reactions requiring immediate medical attention.
- Non-Urgent Medical Procedures: Temporary interruption may be necessary for non-urgent medical procedures that temporarily interfere with the participant's ability to engage with the trial intervention, such as elective surgery or diagnostic procedures.
- Serious Adverse Events: Temporary discontinuation may be indicated in the presence of serious adverse events related to the trial intervention, pending further evaluation and resolution of symptoms.
- Participant Preference: Temporary discontinuation may occur at the participant's request due to personal reasons, travel, or other temporary circumstances that interfere with intervention adherence.

During the period of temporary discontinuation or interruption of trial intervention, the following steps will be taken:

- Documentation: The reason for temporary discontinuation or interruption will be documented in the participant's trial documentation, including the date and duration of interruption.
- Participant Education: Participants will be informed of the temporary discontinuation or interruption and provided with guidance on when and how to resume the intervention, as well as any necessary precautions or restrictions.
- Continued Trial Participation: Participants may continue in the trial during the period of temporary discontinuation or interruption, depending on the nature of the event.
- Assessments: Depending on the nature and duration of the temporary discontinuation, certain trial assessments may continue as scheduled, while others may be temporarily suspended or deferred. Assessments relevant to safety monitoring or primary endpoints will be prioritized, while non-essential assessments may be postponed until the participant resumes the intervention.

Rechallenge

- Participants will be allowed to rejoin the trial if medically permitted.

7.2 Participant Withdrawal from the Trial

1. Voluntary Withdrawal: Participants have the right to withdraw from the trial at any time for any reason without facing any consequences.
2. Inability to Continue: Participants may withdraw if they become unable to continue participating in the trial due to medical reasons, such as worsening health status, or other personal circumstances.
3. Non-compliance: Participants may be withdrawn from the trial if they fail to adhere to the study protocol or follow the instructions provided by the research team.
4. Safety Concerns: Participants may be withdrawn from the trial if there are safety concerns identified during the course of the study, such as the development of

serious adverse events or medical conditions that may compromise their well-being.

7.3 Lost to Follow-Up

1. We will provide clear communication about the importance of follow-up visits with some incentives for participation and maintaining regular contact with participants through phone calls, emails or reminders.
2. Offer flexibility in scheduling
3. Follow up duration will be 4 weeks after a lack of response. We will re-attempt to contact the survivor after a brief 2 week pause after which we will no longer contact the survivor.

Section 8: TRIAL ASSESSMENTS AND PROCEDURES

This section outlines the comprehensive assessments and procedures deployed throughout the trial to ensure accurate, reliable data collection across all specified endpoints, emphasizing adherence to the trial's design and objectives.

Data Collection and Assessment Methods

- Claims Record: To accurately assess the financial impact of the intervention on healthcare expenditures, participants will be requested to provide Claims Records and Explanation of Benefits documentation. This comprehensive data set will encompass costs related to hospitalization, medication, lab visits, and other relevant medical expenses.
- Electronic Health Records (EHR): For a detailed and objective view of medical histories, participants will be asked to access their Electronic Health Records through platforms like MyChart. This step aims to enrich the claims data with additional medical record insights with information like days of hospitalization, disease for which treatment was undertaken, whether it was an Emergency visit or not and so on.
- Patient-Reported Outcomes: In a complementary approach to objective data collection, participants will also self-report on various aspects including healthcare

expenditures, quality of life (measured by FACT-G) and cancer progression status. Furthermore, they will report on absenteeism (detailing the number of leave days taken, including short-term or long-term disability status) and presenteeism (evaluated through work motivation and performance review scores). These self-reported metrics will be securely collected through a digital platform, aiming to supplement and validate the analysis of claims and EHR data.

Live Coaching Consistency

- **Training Program for Live Coaches:** To ensure uniform delivery of the intervention across participants, live coaches will undergo a standardized training program. This program will cover the intervention's core components, ethical guidelines, communication skills, and use of the digital platform for interaction with participants. Regular refresher sessions and assessments will maintain coaching quality and consistency.

Ensuring Data Integrity and Consistency

- **Centralized Data Collection:** Utilizing a centralized digital platform for self-reported data and integrating EHR information will ensure data consistency and facilitate real-time monitoring of trial progress.
- **Standardized Assessments:** All assessments, including all the self-reported metrics, will be conducted following standardized protocols. Instructions on the timing and conditions of assessments will be clearly communicated to participants, and specialized training will be provided to any personnel involved in data collection or analysis.
- **Blinding Maintenance:** While blinding participants to the intervention details is not feasible, measures will be in place to ensure that data analysts and the Trial Monitoring Committee members are blinded to group assignments to minimize bias in outcome assessment and safety monitoring.

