- Specific Instructions: Participants will receive login credentials and instructions for accessing the software upon enrollment in the trial. They will be guided through the process of scheduling and participating in live exercise sessions, including how to navigate the platform and interact with their exercise coach.
- Delayed or Missed Intervention: Participants who miss scheduled exercise coaching sessions will have the opportunity to reschedule or make up missed sessions at a later time within the 12-month intervention period.
- Coaching Modifications: The coaching strategy includes personalized exercise recommendations tailored to each participant's unique needs and physical condition.
 - For instance, in cases of severe fatigue post-chemotherapy, coaches may adapt the program to include gentle activities like simple stretching followed by soothing meditation to ensure participant comfort and safety.
- Start and Stop Treatment: Participants are encouraged to engage consistently in the software app throughout the 12-month intervention period. However, they have the flexibility to start and stop treatment as needed, with the option to resume participation at their discretion.
- Dose Reductions: As this intervention does not involve pharmaceuticals, there are no dose reductions; however, adjustments to the frequency, intensity and approach of exercises may be made in response to participant feedback and progress (as suggested above with examples).

Details for Control Product:

- Timing of Intervention: Participants can log in to the app at their convenience to learn about exercise, diet and meditation guidelines.

- Duration: Participants will have access to the Active Comparator for the same 12-month period as the intervention arm.
- Planned Route of Administration: The Active Comparator will be administered remotely via the online platform, mirroring the administration method of the experimental intervention.
- Specific Instructions: Participants will receive login credentials and instructions for accessing the software upon enrollment in the trial.
- Delayed or Missed Doses: Participants in the control arm are free to manage how they like to use the app within the 12-month intervention period.
- Dose Modifications: N/A
- Start and Stop Treatment: Participants in the control arm have the same flexibility to start and stop treatment as those in the intervention arm, with the option to resume participation at their discretion.
- Dose Reductions: N/A

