9.2 Analyses Supporting Primary Objective(s)

The primary analysis will focus on quantifying the impact of **Complement Theory on changes in Quality of Life Score (QoLS), measured by the FACT-G instrument**, over the trial period. Assessments will occur at baseline, 3, 6, 9, 12, and 18 months.

- **Statistical Model, Hypothesis, and Method of Analysis**

- Primary Estimand (Change in QoLS):
 - Null Hypothesis (H0): There is no difference in the mean change in FACT-G QoLS between participants in the Complement Theory program and those in the control group at specified time points.
 - Alternative Hypothesis (H1): Participants in the Complement Theory program demonstrate a statistically significant improvement in QoLS compared to the control group.
- Baseline Data Analysis: Baseline demographics and characteristics will be provided and summarized in both treatment and control groups. Standardized mean differences (SMDs) will be calculated as the measure of distance between groups. SMDs of 0.2 to <0.5, 0.5 to <0.8 and ≥0.8 are considered small, medium, and large, respectively. Frequencies and percentage will be provided for the binary variables as well as the categorical variables (Yes/No); mean (standard deviation) and median (range) will be computed for continuous variables.
- Method of Analysis: Mixed models for repeated measures (MMRM) will be utilized to analyze changes in FACT-G scores over time, accounting for within-subject correlations. This model allows for the inclusion of both fixed effects and random effects to account for individual variability. In addition, covariate-time interaction terms will be included to guarantee the best results. The strength of the effect from each covariate will be evaluated

through the statistical test significance, i.e., P value, at 95% confidence interval.

- **Handling of Intercurrent Events of Primary Estimand(s)**

- For participants who discontinue the intervention or are non-adherent, we will employ a treatment policy strategy. This means all data collected will be analyzed as per the initial treatment assignment, regardless of the discontinuation or level of adherence, preserving the intention-to-treat principle.

- **Handling of Missing Data**

- Given the potential for missing QoLS data due to dropout or non-response, a multiple imputation (MI) approach will be adopted. The imputation model will incorporate variables predictive of missingness and outcomes to generate plausible values for missing data.

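### Section 7.3 ends outreach about six weeks into silence, so up to five of the FACT-G visits to month 18 go unrequested from people who have not withdrawn consent

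*Protocol*

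**What the plan says.** Protocol section 7.3 sets the contact rule in two steps. First, "Follow up duration will be 4 weeks after a lack of response". Then, "We will re-attempt to contact the survivor after a brief 2 week pause after which we will no longer contact the survivor". It does not define a lack of response. It does not separate people who have withdrawn consent from those who have simply gone quiet, and it does not mention participants on an interruption.

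Other sections of the Protocol bear on this:

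- **Section 9.2, timing.** For FACT-G, "Assessments will occur at baseline, 3, 6, 9, 12, and 18 months".
- **Section 9.2, estimand and missing data.** Discontinuation and non-adherence are handled by a treatment-policy strategy. Missing scores are handled by multiple imputation by chained equations with 10 imputations. The one sensitivity analysis named is per-protocol.
- **Section 6.3.** On the intervention, "they have the flexibility to start and stop treatment as needed, with the option to resume participation at their discretion". No limit on the length of a pause is given.
- **Section 7.1.** "Temporary discontinuation may be warranted in the event of acute medical events such as hospitalization, surgery" is among the foreseen interruptions, and "Participants will be allowed to rejoin the trial if medically permitted". During a temporary interruption, "Assessments relevant to safety monitoring or primary endpoints will be prioritized".
- **Section 11.1.** Loss to follow-up has a 10% tolerance limit, reviewed monthly. It is defined by not continuing to the last planned safety assessment, without revoking consent and without being reached.

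Section 7.3 of the Combined protocol and SAP carries the same contact rule. There the primary endpoint is healthcare expenditure and FACT-G is secondary, so the point below is about the Protocol.

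**The concern.** A treatment-policy estimand needs outcome scores from everyone randomized, including people who have stopped the intervention. Section 7.3 stops asking for those scores long before the last visit, without requiring that the participant has declined to give them. Scores that could have been obtained may then have to be imputed.

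Imputation is sound if the recorded variables explain why scores are missing. In a stage 1 to 4 cancer population, someone silent for six weeks may well be sicker than the recorded data show. If so, imputed values will be too favourable. If the two arms lose different numbers of such people, the treatment contrast is biased. A per-protocol analysis does not test this, because it removes the people concerned.

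**Working it through.** **1. When outreach ends.** Section 7.3 gives 4 weeks plus a 2-week pause: 4 + 2 = 6 weeks, or 6 / 4.345 = 1.4 months. This reads the pause as following the four weeks.

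**2. Visits left unrequested.** The section 9.2 visits are compared with the date outreach ends, assuming the participant does not return unprompted.

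| Silence starts | Outreach ends | Months left to 18 | Section 9.2 visits not requested |
|---|---|---|---|
| Month 1 | 2.4 | 15.6 | 3, 6, 9, 12, 18 (five) |
| Month 3 | 4.4 | 13.6 | 6, 9, 12, 18 (four) |
| Month 6 | 7.4 | 10.6 | 9, 12, 18 (three) |
| Month 9 | 10.4 | 7.6 | 12, 18 (two) |
| Month 12 | 13.4 | 4.6 | 18 (one) |

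Silence starting in the last six weeks before month 18 leaves none unrequested.

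**3. The plan's own sample size.** Section 9.7 inflates 102 completers for 30% dropout: 102 / (1 - 0.30) = 145.7, rounded up to 146. Then 30% of 146 is 43.8, or 44, leaving 102 (51 per arm). The stated figures reproduce.

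**4. Is power the issue for FACT-G?** Section 9.7 assumes means of 70 and 85 and a value of 20, labelled a variance. The stated 42 participants is approached only if 20 is a standard deviation: n per arm = 2 x (1.645 + 0.842)^2 x 20^2 / 15^2 = 22 against the stated 21. With 51 per arm, the standardized difference is 15 / 20 = 0.75 and the expected z is 0.75 x sqrt(51 / 2) = 3.79. One-sided power at 0.05 is Phi(3.79 - 1.645) = 98%. Two-sided it is 97% by the normal approximation and 96% by the noncentral t. The 30% dropout already allowed for leaves FACT-G power high, so power is not the problem.

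**5. Size of a possible bias (assumed values).** Let a fraction d of an arm be lost, and let lost participants score g points lower than those retained. The observed mean then exceeds the full-arm mean by d x g, and the contrast is biased by (d_test - d_control) x g. The documents give neither d by arm nor g.

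| Loss, test / control | g = 5 | g = 10 | g = 15 |
|---|---|---|---|
| 30% / 30% | 0 | 0 | 0 |
| 25% / 35% | -0.5 | -1.0 | -1.5 |
| 20% / 40% | -1.0 | -2.0 | -3.0 |

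The largest entry is 3 / 15 = 20% of the assumed treatment difference. Swapping the arms reverses the sign. These are observed-case shifts from total loss. The share caused by section 7.3 is unknown, and the planned model and imputation would remove whatever part of the shift earlier scores and covariates explain.

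**The case against.** The case for leaving the rule alone has several parts.

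- **Section 7.3 ends outreach, not participation.** It does not withdraw anyone, close the app or bar a return, and section 7.1 allows rejoining. A reader might infer that the missing data are permanent; the text does not support that. What stands is that a return must be unprompted. The documents do not say whether in-app forms continue after contact stops.
- **Pausing the intervention is not silence.** Section 6.3 concerns treatment, and a person can stop coaching and still answer questionnaires. Section 7.1 requires interruptions to be documented and gives priority to primary-endpoint assessments. So 7.3 does not flatly contradict the freedom to pause. It does lack any exemption for such participants, and the section 7.1 safeguard covers recognized interruptions, not unexplained silence.
- **The illness link is inferred.** Section 7.3 applies whatever the reason for silence. Section 7.1 and the population make illness a plausible reason, but no figure is given.
- **So is a difference between arms.** Coach contact could keep test participants responding. Equally, 3 to 5 sessions a week could tire them, and 7.3 promises regular contact without restricting it to one arm. The direction is open.
- **Partial records are used.** The schedule of events collects FACT-G in even-numbered weeks and later every 30 days, so the model and the imputation have earlier scores to draw on. This reduces the problem but does not test it.

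A reader might also claim a power gain from better retention. That would need an assumed fall in dropout that the documents do not support, since section 9.7 attributes the 30% to the length of follow-up. It would matter mainly for Employee Performance and Total Healthcare Expenditure, the rows with a standardized difference of 0.5, and neither is primary.

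**Conclusion.** The concern holds as a gap in endpoint collection. Followed as written, section 7.3 stops requesting primary-endpoint scores about six weeks into silence, without withdrawal of consent, while section 9.2 analyses those scores to month 18 under a strategy that needs them. One to five section 9.2 visits are affected, depending on when silence starts, unless the participant comes back unprompted.

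The consequence is a risk of bias whose size the documents cannot fix. In the assumed scenarios it runs from 0 to 3 FACT-G points. That missingness is not at random is a reasonable inference, not a documented fact. Neither permanent loss, nor illness as the cause, nor a known imbalance between arms, nor a power deficit for FACT-G is established. The change is still worth making, because a score never requested at its visit usually cannot be recovered.

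**What to change.** Replace the final clause of Protocol section 7.3 with wording to this effect:

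> *Non-responders who have not withdrawn consent will continue to receive automated FACT-G requests at months 3, 6, 9, 12 and 18, by the same method in both arms. This section does not end endpoint contact for participants on an interruption under section 6.3 or 7.1.*

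Define a lack of response in the same section. The change concerns data requests only and leaves the rules on pausing or stopping the intervention as they are.

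For section 11.1, keep a provisional count of non-responders so that the monthly 10% limit (14.6 of 146, so crossed at 15 participants) still has something to count. Assign final lost-to-follow-up status as section 11.1 already defines it. Deferring every count to month 18 would leave the limit unable to trigger corrective action in time.

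The cost is one clause and automated messages from the app that, under section 11.2, already hosts the self-report forms. The downside is a few more reminders to people who may not answer. Some scores will still be missing, so the change reduces reliance on untested imputation assumptions but does not remove it.
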